4.1.3 Overall Survival

Overall survival is defined as the time from randomization to the date of death from any cause. If a subject has not died, their survival time will be censored at the date of last contact (“last known alive date”). A subject will be censored at the date of randomization if they were randomized but had no follow-up.

[REDACTED]

[REDACTED]

[REDACTED]

[REDACTED]

[REDACTED]

5 SAMPLE SIZE AND POWER

The number of events and power for PFS were calculated assuming an exponential distribution for each arm. One interim analysis of PFS is planned, and will allow for early stopping for superiority. An O'Brien and Fleming α spending function will be employed to determine the stopping boundaries.

Approximately 750 subjects will be randomized to the two treatment groups in a 1:1 ratio in order to obtain at least 482 progression events i.e. documented progressions or deaths. Four hundred and eighty-two events ensures that a two-sided 5% level sequential test procedure with one interim analysis will have 90.5% power if the median PFS times in the control and experimental arms were 25 and 33.75 months respectively; i.e. if the hazard ratio (HR) of the experimental arm to the control arm is 0.74.

The interim analysis of PFS will be conducted after 70% of the total events (i.e., at least 338 of the planned 482 events) have been observed.

Assuming an accrual rate of 24 subjects per month, it will take approximately 60 months to obtain the required number of events; 31 months of accrual and 29 months for PFS follow-up. At the time of final PFS analysis, an observed HR of 0.84 or less (which corresponds to a 4.8 months or greater improvement in median PFS (25 vs 29.8 months), would result in a statistically significant difference between the two treatment arms.

Survival, a key secondary endpoint, will be formally compared between the two arms at the time both ORR and PFS analyses are positive (whether that occurs after 70% of PFS events or all 482 events) and again after at least 354 deaths have been observed, which is expected to occur 7 years (84 months) after the initiation of the study. An O'Brien and Fleming α -spending function will be used to obtain the nominal significance level for the interim and final analysis of survival. Three hundred and fifty-four deaths ensure that a two-sided, $\alpha=0.05$ level test procedure with one interim analysis will have 80% power to detect a 8.7 percentage point improvement in the 4-year survival rate¹ (from 59% to 67.7%, i.e. a HR= 0.74).

Power calculations were performed using East v5.1.

6 STUDY PERIODS, TREATMENT REGIMENS AND POPULATIONS FOR ANALYSES

6.1 Study Periods

There are three periods in this study: screening, on-treatment and post-treatment follow-up.

Screening: Most screening procedures must be done no more than 14 days prior to randomization. Some exceptions include efficacy assessments and ECGs, which can be done up to 28 days prior to randomization. See Section 5 of the Protocol for full details of study procedures and timings. For analyses purposes data collected within 60 days of randomization and prior to first dose will fall into the screening/baseline period. Site personnel should make every effort to initiate study drug treatment within three days after randomization.

On-Treatment Period: The on-treatment period has three phases: the first two cycles, cycles 3-18, and cycle 19 and beyond. All cycles are 28 days in duration. The first two cycles are characterized by weekly visits, safety assessments, and, in the experimental arm, elotuzumab infusions. Cycles 3-18 are characterized by fortnightly visits, safety assessments and, in the experimental arm, elotuzumab infusions. Cycles 19 and beyond, are characterized by once every 4 weeks visit, safety assessments and, in the experimental arm, elotuzumab infusions. Subjects should have myeloma urine and serum laboratory assessments every four weeks while on treatment until they progress and should have imaging for extramedullary plasmacytomas, if indicated, and at the time of CR/sCR assessment. The timing of the tumor assessments will be independent of dosing. Study treatment ends when the subject progresses, experiences unacceptable toxicity, or withdraws consent.

Follow-up Period: Subjects who discontinue study therapy prior to progression must continue to undergo tumor assessments on the same schedule used in the on-treatment period, regardless of whether they are receiving new anti-myeloma therapy. The only exception to this is if the subject withdraws consent for all study procedures or loses the ability to consent freely.

Follow-up for survival and subsequent myeloma therapy will be conducted every 16 weeks until the subject dies or the study ends.

6.2 Treatment Regimens

Subjects will be randomized to one of two treatment arms, E-Ld or Ld. Subjects will receive these treatments in 28-day cycles until disease progression, unacceptable toxicity or withdrawal of consent.

On Arm A (E-Ld) subjects receive:

- Elotuzumab: 10 mg/kg intravenous (IV) on Days 1, 8, 15 and 22 of the cycle during Cycles 1 and 2; Days 1 and 15 during Cycles 3-18; and 20mg/kg intravenous (IV) on Day 1 of the cycle during subsequent cycles.
- Lenalidomide: 25 mg orally (po) on Days 1-21 of each cycle.
- Dexamethasone: Administered on Days 1, 8, 15 and 22 of cycle. 28 mg po + 8 mg IV whenever given prior to elotuzumab; 40 mg po on weeks on which no elotuzumab is given.

On Arm B (Ld) subjects receive:

- Lenalidomide: 25 mg po on Days 1-21 of each cycle.
- Dexamethasone: 40 mg po on Days 1, 8, 15 and 22 of each cycle.

6.3 Populations for Analyses

The following subject populations will be used for the statistical analysis:

All enrolled subjects: All subjects who gave signed informed consent and who were entered in the IVRS.

Randomized subjects: All enrolled subjects who were randomized.

Treated subjects: This population includes all randomized subjects who received at least one dose of study medication (lenalidomide, dexamethasone or elotuzumab).

The analysis of baseline characteristics, efficacy and subject-reported outcomes will be carried out on the “Randomized subjects” population, with subjects grouped according to the treatment arm to which they were randomized. The analysis of extent of exposure and safety will be based on the “Treated subjects” population, with subjects grouped according to the treatment received, where treatment received is defined as the treatment arm to which they were randomized, unless they received the wrong treatment throughout the study.

7 STATISTICAL ANALYSES

7.1 General Methods

Continuous variables will be summarized using descriptive statistics; i.e. number of non-missing observations (n), mean, standard deviation (STD), median, minimum, maximum, first quartile and third quartile. Categorical variables will be summarized by frequencies and percentages. Minimum and maximum values will be reported to the precision as the data collected; mean, median and quartiles will be rounded to one decimal place more than the data collected; STD will be rounded to one decimal place more than the summary statistic (e.g. mean) for which it is calculated, and percentages will be rounded to one decimal place. Percentages greater than zero but less than 0.1 will be presented as “<0.1”.

The Kaplan-Meier (KM) product limit method will be used to estimate the distribution and median of each time-to-event endpoint in which censoring is involved. The Brookmeyer and Crowley method⁹ will be used to compute a 95% confidence interval (CI) for the median of each time-to-event endpoint using the log-log transformation of the survivor function $S(t)$.

The stratified log-rank test will be performed to compare time to event distributions (PFS or OS) between treatment groups. Stratification factors will be obtained from IVRS randomization dataset. The stratified log-rank test will be based on the ‘proc lifetest’ procedure in SAS 9.2, in which the ‘strata statement’ specifies the stratification factors with ‘group option’ equal to randomized group.

A stratified Cox proportional hazards model will be used to compute an estimate of, and CI for, the hazard ratio of the investigational to the control arm, for each endpoint. Medians and hazard ratios for time-to-event variables will be rounded to two decimal places.

The main analyses of tumor response and progression-free survival will be conducted using the best overall response, date of response, and date of progression assigned by the IRC.

Laboratory results, adverse events, and other symptoms will be graded using the National Cancer Institute (NCI) Common Terminology Criteria for Adverse Events (CTCAE), Version 3.0, except where CTCAE grades are not available. Individual laboratory values will be presented in both the conventional US units and the International System of Units (SI). Adverse events will be

categorized using the most current version of Medical Dictionary for Regulatory Activities (MedDRA), by system organ class and preferred term. Prior therapies will be summarized using the most current version of the World Health Organization (WHO) drug dictionary.

Statistical analyses will be carried out in SAS (Statistical Analysis System, SAS Institute, North Carolina, USA), unless otherwise indicated.

7.2 Study Conduct

7.2.1 Accrual Patterns

Tables summarizing accrual by center, country, region (North America, European Union, and Rest of World) overall and by treatment group will be generated (see [appendix 2](#) for a list of countries in each region). Subject accrual will also be summarized by the randomization stratification factors per IVRS (Stage of disease [ISS 1 – 2 versus 3], Age [< 75 years old versus ≥ 75 years old], ECOG Performance status [0 versus 1 – 2]), overall and by treatment group. In addition, this summary will also be presented based on the stratification information obtained from the baseline CRF pages. A cross tabulation of IVRS vs. baseline stratification factors will also be summarized.

7.2.2 Protocol Violations

A relevant protocol deviation is defined as a deviation from the protocol which is programmed in the database and which could potentially affect the interpretability of the study results.

The number and percentage of subjects with any relevant protocol deviation and each specific deviation will be presented overall and by treatment group.

The following eligibility deviations are considered relevant in this study and will be summarized for all randomized subjects:

1. Any prior systemic anti-myeloma therapy
2. Non-measurable disease. This occurs when none of the following three conditions are met:
 1. IgG, IgA, or IgM M-protein ≥ 0.5 g/dL
 2. Serum IgD M-protein ≥ 0.05 g/dL
 3. M-protein ≥ 200 mg in 24-hour urine.
3. No baseline tumor assessment. This occurs when there are no tumor assessments at all (laboratory assessments) on or prior to first day of dosing. See [section 4.1.1.1](#), for definition of adequate tumor assessment.

Also, the following on-treatment deviations are considered relevant in this study and will be summarized for all treated subjects:

4. Non-protocol specified systemic anti-myeloma therapy prior to discontinuation of study therapy
5. Received non-assigned treatment regimen throughout the study.

6. Subjects continuing to receive study therapy after 10 weeks of first documented progression per investigator (as progression should be confirmed).

If assessments based on the central laboratory is unavailable, but the local laboratory results are available, then those will be used for evaluating deviations 2 and 3.

A by subject listing of relevant protocol deviations will be provided.

7.3 Study Population

7.3.1 Subject Disposition

A frequency table of enrolled subjects, broken down by whether or not they were randomized, and the reasons for not being randomized, will be produced.

Subject disposition during the treatment period will be summarized, overall and by treatment group. The number and percentage of subjects randomized, treated, still on treatment and discontinued from the treatment will be presented.

By-subject listings will also be produced to accompany the tables on enrollment and the subject disposition table.

In addition, a by-subject listing indicating whether the subject was included in each of the analysis populations will be provided.

7.3.2 Demographic and Subject Characteristics

Demographic and baseline characteristics will be summarized, overall and by treatment group. The following parameters will be summarized; age at the time of informed consent (years), age category at time of informed consent (<65 years, ≥65 years), and (<75 years, ≥75 years), gender (Male, Female), race (White, Black/African American, American Indian/Alaska Native, Asian, Native Hawaiian/Other Pacific Islander, Other), ethnicity – for US subjects only (Hispanic/Latino, Not Hispanic/Latino), weight (kg) and ECOG performance status (0,1,2) .

An accompanying by-subject listing of demographic and subject characteristics will be presented.

7.3.3 Disease Characteristics at Baseline

Baseline disease characteristics will be summarized, overall and by treatment group. The following parameters will be presented to summarize baseline disease:

- Serum M-protein (g/dL)
- Urine M-protein (mg/24 hours)
- Myeloma type (IgG, IgA, IgD, IgM, Light chain disease)
- Number of lytic bone lesions (0, 1-3, >3)
- Myeloma risk category
 - High risk: ISS stage II or III **and** t(4;14) or del(17p) abnormality

- Low risk: ISS stage I or II **and** absence of t(4;14), del(17p) and 1q21 abnormalities and age < 55 years
 - Standard risk: any subjects not meeting the definition of high or low risk.
 - Not Evaluable: Subjects having missing data preventing the classification in the other 3 categories
- Individual FISH /Cytogenetic abnormalities (del 17p, t(14; 16), t(4; 14), and del 13)
 - $\beta 2$ microglobulin (mg/L) (<3.5, ≥ 3.5 -5.5, ≥ 5.5)
 - Albumin (g/L) (<3.5, ≥ 3.5)
 - LDH (<300 IU/L, ≥ 300 IU/L)
 - Soft tissue plasmacytomas (Yes, No)
 - ISS Stage at enrollment (I, II, III)
 - Time from disease diagnosis to randomization (months)

An accompanying by-subject listing of disease characteristics at baseline will be presented.

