APPENDIX 1 INTERNATIONAL STAGING SYSTEM

Stage	Criteria	Median Survival (months)
I	Serum β_2 -microglobulin < 3.5 mg/L Serum albumin \geq 3.5 g/dL	62
II	Not stage I or III ^a	44
III	Serum β_2 -microglobulin \geq 5.5 mg/L	29

^a There are two categories for stage II: serum β_2 -microglobulin < 3.5 mg/L but serum albumin < 3.5 g/dL; or serum β_2 -microglobulin 3.5 to < 5.5 mg/L irrespective of the serum albumin level.

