8.7 Topline Analyses

Outputs covering the following topics will be included in the top-line analyses:

Study conduct:

- Relevant protocol deviations (Table and Listing)

Subject population:

- End of Treatment Summary
- Accrual by Region
- Accrual by stratification factors at randomization
- Demographic Characteristics Summary
- IVRS Stratification Factors Summary
- Baseline Myeloma Characteristics Summary (SI units)
- Other Baseline Laboratory Measurements Summary
- Baseline Myeloma (Cytogenetics and FISH) Risk Factors Summary
- Time from Diagnosis to Randomization Summary
- Baseline Physical Measurements Summary

Extent of exposure:

- Number of Cycles Summary

- Elotuzumab Dose Intensity Summary
- Dexamethasone Dose Intensity Summary
- Lenalidomide Dose Intensity Summary
- Elotuzumab Delay Summary
- Elotuzumab Omission Summary
- Elotuzumab Infusion Interruption Summary
- Lenalidomide Reduction Summary
- Lenalidomide Interruption Summary

Progression free survival:

- Currentness of Follow-Up for PFS (IRC, ITT definition) Summary
- PFS (IRC, Primary Def.) Analysis
- Kaplan-Meier plot of PFS (IRC, Primary Def.)
- PFS (IRC, Primary Def.) Analysis Adjusting for Different Baseline Covariates
- PFS (IRC, Primary def.) Hazard Ratio and 95% CI in Subsets (Forest plot)
- PFS (IRC, ITT Analysis)
- Kaplan-Meier plot of PFS (IRC, ITT)
- PFS (IRC, ITT) Analysis Adjusting for Different Baseline Covariates
- PFS (IRC,ITT) Hazard Ratio and 95% CI in Subsets (Forest plot)
- Kaplan-Meier plot of PFS (Inv., Primary Def.)
- Kaplan-Meier plot of PFS (Inv., ITT.)
- Concordance of PFS between the IRC and investigator
- Concordance and Timing of PFS per IRC and Investigator
- Assessment of Censoring Distributions with Reverse Kaplan Meier Plot of PFS (IRC, Primary Def.)
- Assessment of Censoring Distributions with Reverse Kaplan Meier Plot of PFS (IRC, ITT Def.)

Tumor response:

- Best Overall Response (IRC)
- Best Overall Response (Inv)
- Best Overall Response (IRC) Modified for Subsequent Therapy
- Best Overall Response (IRC) Odds Ratio and 95% CI in Subsets (Figure)
- Cross Tabulation of Modified Best Overall Response per IRC and Investigator
- Time to First Response (IRC) Summary
- Kaplan-Meier Plot of Duration of Response (IRC)

Overall survival (only when interim PFS and ORR analyses are positive):

- Currentness of Follow-Up for Overall Survival Summary Overall Survival Analysis
- Overall Survival Analysis Adjusting for Different Baseline Covariates

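### Two descriptive category rules in the SAP are wrong as written: the middle safety age band (SAP 7.6.3) contains the whole under-65 band, and the baseline albumin cut (SAP 7.3.3) carries the wrong unit

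*SAP*

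**What the plan says.** **Safety age bands.** SAP 7.6.3 (Safety by subgroups) lists three: below 65; a middle band printed as less than 65 up to less than 75; and 75 or older. They apply to adverse events with at least 5% frequency, adverse events leading to discontinuation, serious adverse events, deaths within 60 days of last dose, second primary malignancies and infusion reactions.

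**Albumin.** SAP 7.3.3 (Disease Characteristics at Baseline) prints "Albumin (g/L) (<3.5", with 3.5 or more as the other category. Protocol Appendix 1 defines one route into ISS stage II as beta-2 microglobulin below 3.5 mg/L "but serum albumin < 3.5 g/dL".

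**Units.** SAP 7.1 states: "Individual laboratory values will be presented in both the conventional US units and the International System of Units (SI"). The topline list in SAP 8.7 includes "Baseline Myeloma Characteristics Summary (SI units").

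**Beta-2 microglobulin.** SAP 7.3.3 starts the bands as "microglobulin (mg/L) (<3.5", then has a band from 3.5 to 5.5 with no sign on its upper end, then 5.5 or more. Appendix 1 gives the middle range as "3.5 to < 5.5 mg/L irrespective of the serum albumin level".

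**The concern.** These are rules for building tables, so a programmer who follows them literally produces wrong or empty output.

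- For age, the safety subgroup tables would hold two nested groups and one separate group in place of three disjoint groups. Age 65 is also the boundary on which transplant ineligibility by age rests in the inclusion criteria, so the 65 to 74 group is one a reader will look for.
- For albumin, a cut ten times too low separates no one, and the row cannot describe balance between the arms at the ISS threshold.
- For beta-2 microglobulin, the ambiguous value is the one at which Appendix 1 starts stage III.

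**Working it through.** **1. Age bands in SAP 7.6.3, applied literally**

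| Age | Below 65 | Middle band as printed (below 75) | 75 or older |
|---|---|---|---|
| 60 | yes | yes | no |
| 64 | yes | yes | no |
| 65 | no | yes | no |
| 70 | no | yes | no |
| 74 | no | yes | no |
| 75 | no | no | yes |
| 80 | no | no | yes |

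Let n1, n2 and n3 be the numbers of treated subjects aged below 65, 65 to 74, and 75 or older. The printed bands hold n1, n1 + n2 and n3 subjects. Their sum is (n1 + n2 + n3) + n1, so the double count equals the whole under-65 group. The documents give no age distribution, so n1 cannot be stated. The overlap is among subjects under 65; age 65 itself falls in the middle band only.

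The baseline age categories do not share this fault. SAP 7.3.2 uses two separate dichotomies, the first starting "age category at time of informed consent (<65 years" and the second at 75. The only age rule in SAP 7.3.3 is the single cut in the low-risk definition, "1q21 abnormalities and age < 55 years".

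**2. Albumin cut in SAP 7.3.3**

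- Conversion: 1 g/dL = 10 g/L.
- Appendix 1 cut: 3.5 g/dL × 10 = 35 g/L.
- SAP cut as labelled: 3.5 g/L ÷ 10 = 0.35 g/dL.

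The SAP's number agrees with Appendix 1 only if the unit is g/dL. In the printed unit it is low by a factor of 35 / 3.5 = 10.

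| Albumin, g/dL | g/L | SAP rule as printed, on g/L data | ISS cut at 35 g/L |
|---|---|---|---|
| 0.5 | 5 | ≥3.5 | <35 |
| 2.0 | 20 | ≥3.5 | <35 |
| 3.0 | 30 | ≥3.5 | <35 |
| 3.4 | 34 | ≥3.5 | <35 |
| 3.5 | 35 | ≥3.5 | ≥35 |
| 5.0 | 50 | ≥3.5 | ≥35 |

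On g/L data, a subject reaches the lower category only with albumin below 0.35 g/dL. On g/dL data, the split is the intended one and only the printed unit is wrong.

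**3. Beta-2 microglobulin**

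Reading the middle band as inclusive of 5.5: 3.4 falls in the first band only; 3.5 and 5.4 in the middle only; 5.5 in both the middle and the top; 5.6 in the top only. One boundary value is ambiguous. If the middle band is read as exclusive, nothing overlaps.

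**The case against.** **Evident slips.** With below 65 on one side and 75 or older on the other, the middle age band is plainly meant to be 65 to below 75, and a programmer would probably see that. A symbol could also have been lost in conversion from PDF; a look at the SAP itself settles this, although the next line shows its ≥ sign correctly. Even under the literal rule, counts for ages 65 to 74 could be recovered by subtracting the first band from the second wherever both show the event. This makes the problem small, but it does not make the rule right.

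**The albumin unit is not settled.** SAP 8.6 makes laboratory tables available in both SI and US units, and SAP 7.3.3 itself gives serum M-protein in g/dL. The SI label in SAP 8.7 belongs to one topline output. The same list has a separate output for other baseline laboratory measurements, and the specific tables are left to a Data Presentation Plan. A reader might infer that all subjects will fall in one category. The documents support this only on the condition that the cut is applied to g/L data. That objection stands.

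**Stratification.** A reader might infer that the albumin error undermines the ISS randomization factor or the check on it. It does not. The factor is ISS 1-2 versus 3, and in Appendix 1 stage III depends on beta-2 microglobulin alone. Albumin separates stage I from II, which the factor pools. ISS stage I, II and III has its own row in SAP 7.3.3, and nothing in the SAP derives it from the albumin row. SAP 7.2.1 plans a cross-tabulation of IVRS against baseline stratification factors. SAP 7.3.5 also tabulates baseline albumin by CTC grade and arm, so albumin balance would not go unseen.

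**Efficacy.** A reader might infer some effect on the primary or key secondary results. SAP 7.1 and 7.5 take the strata from IVRS, and none of these rows enters a test.

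**Conclusion.** Two rules are wrong as written and one needs a small alignment.

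- **Safety age band:** read literally, all subjects under 65 are counted in two of three bands and ages 65 to 74 are never reported alone. This assumes only that the printed sign is what the SAP says. It is the more consequential item, because it governs several safety outputs.
- **Albumin:** the number and unit contradict Appendix 1 by a factor of 10. If applied to g/L data, essentially all subjects fall in the upper category. This assumes that no one has albumin below 0.35 g/dL; the documents give neither an albumin distribution nor an albumin eligibility limit. If the data are in g/dL, it is a labelling error only.
- **Beta-2 microglobulin:** one boundary value, 5.5 mg/L, is ambiguous, and only on an inclusive reading.

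The effect stops at descriptive baseline and safety subgroup tables. PFS, ORR and OS inference, power, alpha and event counts are unaffected. It is worth correcting before tables are programmed, as a minor point.

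**What to change.** Change three lines of the SAP, and carry the same wording into the Data Presentation Plan:

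1. SAP 7.6.3: age <65, ≥65 to <75, ≥75 years.
2. SAP 7.3.3: albumin <35, ≥35 g/L (equivalently <3.5, ≥3.5 g/dL), matching Appendix 1.
3. SAP 7.3.3: beta-2 microglobulin <3.5, 3.5 to <5.5, ≥5.5 mg/L, matching Appendix 1.

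If table programs already exist, check that they use these limits and that the albumin cut matches the unit of the analysis dataset. No new data are needed, and the design and the planned tests do not change.
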